1.4.2. Phase 1 Study in Patients With Chronic Kidney Disease (COR-001-SC1)

[figure not shown]
This study was a Phase 1, randomized, double-blind, placebo-controlled, cohort dose-escalation study in patients with CKD to assess the safety, PK, and pharmacodynamics (PD) of a single dose of Ziltivekimab. The study population had moderate-to-severe CKD (ie, eGFR 20 to 60 mL/min/1.73 m²) who had serum CRP levels >2 mg/L over 2 consecutive measurements. The primary objective evaluated the safety of single SC doses of Ziltivekimab (planned doses of 5, 15, 50, and 100 mg). The main secondary objective evaluated single-dose PK of SC Ziltivekimab and the effects of Ziltivekimab on CRP and serum amyloid A (SAA).

After SC administration, Ziltivekimab concentrations reached peak levels by 7 to 17 days after dosing, on average, and serum Ziltivekimab concentrations remained quantifiable up to 217 days

postdose in all patients. Ziltivekimab concentrations increased in a dose-dependent manner. Terminal slopes (half-life) appeared similar for the 5 and 15 mg doses, suggesting linear PK. High intersubject variability among the 3 patients in the highest dose cohort (50 mg) confounded the interpretation for that dose. One patient in the 50 mg dose cohort had levels 2- to 3-fold higher than the other 2 patients so that it appeared that the latter patients displayed a less than dose proportional increase, while the former showed a greater than dose proportional increase in Ziltivekimab serum levels.

Mean hs-CRP levels were comparable and elevated at Baseline across placebo and the Ziltivekimab treatment groups, suggesting systemic inflammation. Figure 2 presents the percentage of patients who achieved an hs-CRP level of <2.0 mg/L from Baseline to Week 32. A consistent decrease in hs-CRP levels was observed in the Ziltivekimab dose groups throughout the first 8 weeks post randomization, while levels in the placebo group increased over time.

Figure 1 Percentage of Chronic Kidney Disease Patients Treated With Ziltivekimab or Placebo Who Achieved a High-Sensitivity C-Reactive Protein Level of <2.0 mg/L From Baseline to Week 32

hs-CRP = high-sensitivity C-reactive protein.

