3. STUDY DESCRIPTION

3.1. Summary of Study Design

This is a randomized, double-blind, placebo-controlled study designed to evaluate the efficacy, safety, and PK of Ziltivekimab at 2 dose levels (15 mg or 30 mg) compared to placebo in Japanese patients with Stage 3 to 5 NDD-CKD and evidence of inflammation.

The study will consist of 3 periods: a Screening Period, a Treatment Period, and a Safety Follow-Up Period. The total study duration for each patient will be approximately 6 months.

- Screening Period: up to 2 weeks (Days -14 through -1)

The Screening Period starts on the date of informed consent, and this date will also be the date of the Initial Screening Visit.

- Treatment Period: 12 weeks (Baseline [Day 1] through Week 12)

The Treatment Period starts with the administration of study drug/randomization (Day 1).

- Safety Follow-Up Period: 8 weeks (Weeks 12 through 20)

The Safety Follow-Up Period starts 12 weeks after randomization.

Patients will undergo a Screening Period of up to 14 days, during which the inclusion and exclusion criteria will be evaluated. Patients who meet all inclusion criteria and no exclusion criteria will be randomized 1:1:1 to Ziltivekimab 15 mg, Ziltivekimab 30 mg, or placebo (12 patients per group) for a 12-week Treatment Period. Approximately 36 patients will be randomized. Patient randomization will be stratified by CKD stage which is stratified into two categories: (1) Stage 3 and (2) Stages 4 and 5.

After the Screening Period, patients will be randomized on Day 1. Randomized patients will receive multiple doses of study drug, and the initial dose of study drug should be administered after all assessments are conducted. Patients will then be followed for efficacy and safety through Week 12 and followed for safety in the Safety Follow-Up Period from Weeks 12 through 20. The primary endpoint evaluation will take place at the End of Treatment (using the average of Week 10 and Week 12 assessments).

Patients will be carefully monitored for 1 to 2 hours at the site post every dosing.

Study visits will follow the Schedule of Procedures (Appendix A).

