4. SELECTION AND WITHDRAWAL OF PATIENTS

4.1. Inclusion Criteria

After signing an ICF approved by the Institutional Review Board (IRB) or Independent Ethics Committee (IEC), in order to be eligible, potential patients must meet all of the following criteria:

1. Age ≥ 20 years at the time of signing the ICF;
2. Stage 3 to 5 NDD-CKD, ie, eGFR >10 and <60 mL/min/1.73 m² using the CKD-EPI (Chronic Kidney Disease Epidemiology Collaboration) creatinine equation;¹³
3. Serum hs-CRP level ≥ 2.0 mg/L measured during the Screening Period.

Note: Targeting patients with a history of advanced stage CKD, ASCVD, anemia, diabetic retinopathy, obesity, or elevated body mass index (BMI), and diabetes for Screening will help increase the chances of identifying patients with hs-CRP ≥ 2.0 mg/L;

4. The patient agrees to comply with the contraception and reproduction restrictions of the study as follows (Appendix C):
 - a. Women of childbearing potential must be using a method of contraception that is “highly effective” (ie, $<1\%$ failure rate) for at least 3 months following the last dose of study drug;
 - b. Postmenopausal women must have had no menstrual bleeding for at least 1 year before initial dosing and either be over the age of 60 years or have an elevated plasma follicle-stimulating hormone (FSH) level (ie, >40 mIU/mL) at Screening;
 - c. Women of childbearing potential must have a documented negative serum pregnancy test result at Screening.; and
 - d. All male patients, from the day of dosing until the final study visit, unless surgically sterile, must be willing to use a condom with a partner (male patients with partners of childbearing potential must be willing to use 2 effective methods of birth control, 1 should be condom with spermicide) to prevent pregnancy and drug exposure of a partner, and refrain from donating sperm or fathering a child; and
5. The patient must be willing and able to provide informed consent and abide all study requirements and restrictions.

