3.4.2 Exploratory Efficacy Endpoints

The exploratory analysis variables measuring change or percent change (as applicable) from baseline to end of treatment will be summarized and analyzed in the same manner as the primary analysis variable (section [3.4.1](#)).

For the continuous efficacy variables, the observed values, change from baseline, and percent change from baseline (as applicable) will be summarized by treatment group using descriptive statistics using ITT population.

For binary endpoints (proportions), proportions of patients and 95% CI for proportions will be based on the normal approximation to binomials. The differences in proportions and 95% CIs for differences for each active group will also be presented.

The sample SAS code for normal approximation of binary endpoints and to calculate differences in proportions and 95% CIs can be found below:

```
*****;  
*Note: ACHIEVE = status of patients achieving endpoint (1 if Yes, 2 if No)  
* TRT = Treatment Group  
*****;  
proc freq data=endpoint;  
by TRT;  
tables ACHIEVE / binomial (Wald exact);  
ods output BinomialCLs=CL BinomialProp=Proportion;  
  
run;  
  
proc freq data=endpoint (where=(trtpn in (#,#));  
table trt*RESPONSE / riskdiff;  
output out=proportion_diff RDIF2 ;  
  
run;
```

The following exploratory efficacy endpoints will be analyzed:

- Difference in the proportion of patients achieving hs-CRP response, defined as hs-CRP < 2.0 mg/L, at End of Treatment (average of Week 10 and Week 12) between each active group and placebo.
- Difference in the percent change in fibrinogen, SAA, NT-pro-BNP, change in hemoglobin and change in albumin from Baseline to End of Treatment (average of Week 10 and Week 12) between each active group and placebo.

- Difference in the percent change in TC, LDL-C, HDL-C, and TG from Baseline to End of Treatment (average of Week 10 and Week 12) between each active group and placebo.

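### The SAP 3.4.2 sample code would report an arm with no hs-CRP responders as 100% response instead of 0%, because the response level is not fixed

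*SAP*

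**What the plan says.** SAP 3.4.2 lists the proportion of patients with hs-CRP below 2.0 mg/L at End of Treatment as its first exploratory endpoint, compared between each active group and placebo. The prose asks for proportions and differences with 95% intervals by the normal approximation.

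The sample code has two blocks.

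- **By-arm proportions.** The code note defines "ACHIEVE = status of patients achieving endpoint (1 if Yes, 2 if No"). PROC FREQ is run by TRT with "tables ACHIEVE / binomial (Wald exact"), and the results are saved with "ods output BinomialCLs=CL BinomialProp=Proportion". There is no `LEVEL=` option and no `WEIGHT ... / ZEROS` step.
- **Differences.** A second PROC FREQ uses "table trt*RESPONSE / riskdiff" and outputs RDIF2. The variable RESPONSE is not defined in the code note.

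On the setting, Protocol 3.1 has patients "randomized 1:1:1 to Ziltivekimab 15 mg, Ziltivekimab 30 mg, or placebo (12 patients per group"). Protocol 4.1 requires "Serum hs-CRP level ≥ 2.0 mg/L measured during the Screening Period". Protocol 1.4.2 says that in the earlier single-dose CKD study hs-CRP fell on Ziltivekimab "while levels in the placebo group increased over time".

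**The concern.** With BY processing, each arm is its own one-way table. BINOMIAL without `LEVEL=` gives the proportion in the first level that the table contains. As coded, that is Yes only if the arm has at least one responder. If it has none, the sole level is No, and the saved estimate and interval describe non-response while sitting where the response rate belongs.

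Placebo is the arm at risk. It is small, patients enter at or above the response threshold, and placebo hs-CRP did not fall in the earlier study. If the case arose and went unnoticed, the table would show every placebo patient responding, next to a difference that implies none did. The 2.0 mg/L cut-off is also the threshold on which Protocol 1.1.3 and 1.1.4 build the rationale, so this table will be read.

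**Working it through.** The documents state no figure for this endpoint to reproduce. The check has three parts. The software default is applied as a rule and was not executed in SAS.

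**1. What the code reports, by number of responders.** Inputs: n = 12 (Protocol 3.1); Yes = 1, No = 2 (SAP 3.4.2). Rule: report the lowest level present.

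| Responders of 12 | Level reported | Reported rate | Correct rate |
|---|---|---|---|
| 0 | 2 (No) | 100% | 0% |
| 1 | 1 (Yes) | 8.3% | 8.3% |
| 2 | 1 (Yes) | 16.7% | 16.7% |
| 6 | 1 (Yes) | 50% | 50% |
| 11 | 1 (Yes) | 91.7% | 91.7% |
| 12 | 1 (Yes) | 100% | 100% |

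Only the first row is wrong.

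**2. The intervals in that row.**

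- Wald: p ± 1.96 × √(p(1 − p)/n). At p = 1 or p = 0 the root is zero, so the code gives 100–100% and the correct version 0–0%.
- Exact (Clopper-Pearson): for 12/12 the lower limit is 0.025^(1/12) = 0.735, giving 73.5–100%. For 0/12 the upper limit is 1 − 0.735 = 0.265, giving 0–26.5%.

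**3. How likely the row is on placebo.** P(no responders) = (1 − r)^n. The true placebo rate r is an assumption, because the documents give none.

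| Assumed r | n = 12 | n = 10 evaluable |
|---|---|---|
| 2% | 0.785 | 0.817 |
| 5% | 0.540 | 0.599 |
| 10% | 0.282 | 0.349 |
| 15% | 0.142 | 0.197 |
| 20% | 0.069 | 0.107 |
| 25% | 0.032 | 0.056 |
| 30% | 0.014 | 0.028 |

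**Sign of the difference.** RDIF2 is the column 2 proportion in row 1 minus that in row 2. SAP 3.4.1 treats placebo as TRT 1, both in the Hodges-Lehmann reference class and in the mixed-model estimate statements. If RESPONSE carries the coding given for ACHIEVE, column 2 is No, and

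RDIF2 = P(No | placebo) − P(No | active) = [1 − P(Yes | placebo)] − [1 − P(Yes | active)] = P(Yes | active) − P(Yes | placebo).

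That is the intended direction. The two-arm table holds both columns as soon as one patient in either arm responds and one does not, so an empty placebo responder cell does not distort the difference.

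**The case against.** The case for leaving this alone has several parts.

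- **It is illustrative code.** SAP 3.4.2 labels it as a sample, it still contains placeholders, and SAP 6 defers detailed programming specifications to a separate document. The prose states the intended quantity clearly. This stands: no analysis choice is wrong, and the defect is one of implementation.
- **The trigger may be uncommon.** Entry rests on a screening value, and results of 1.5 to below 2 mg/L are to be retested (Protocol 6.2.1), so patients near the threshold can qualify and drift below it on placebo. The earlier study required two consecutive values. Rising placebo levels are also not the same as a low share below 2.0 mg/L. This stands too, and is why the range above runs to 30%, where the chance is about 1%.
- **It could be caught.** SAP 3.4 separately asks for the number and percentage for categorical efficacy variables, which would show 0 (0%) beside the 100%. PROC FREQ output identifies the level used, and SAP 4.3 and 4.4 provide a pre-final review. These safeguards limit the harm, but they do not make the code right.

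In the other direction, a reader might infer that the treatment difference is also inverted, or that RDIF2 has the wrong sign. The documents do not support that. The difference comes from its own step, and its sign is as intended under the only coding the SAP documents. A reversed sign would need a 0/1 coding of RESPONSE that appears nowhere in the SAP.

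**Conclusion.** The by-arm code is wrong as written for one outcome: an arm with no responders. Then 100% is reported in place of 0%, with the intervals shown above. Every other outcome is reported correctly.

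This rests on the PROC FREQ default for BINOMIAL and on a placebo rate that has to be assumed. It would be too strong to say that the placebo rate will be misreported: the chance is better than even at an assumed 5% and slight at 30%.

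Only the by-arm rate and its interval are touched. The between-group difference is sound. The endpoint is exploratory and lies outside the sequential testing procedure, which covers the primary endpoint only. Severity is low, and the correction is worth making because it is specific and cheap.

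Fixing the level would expose a related limitation. The normal-approximation interval named in the prose has zero width at 0% or 100%, so in exactly this case only the exact interval, which the code already requests, is informative.

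**What to change.** In SAP 3.4.2:

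1. Build a count data set with one record per arm and ACHIEVE level, including zero counts. Run the by-arm step with `weight COUNT / zeros;` and `binomial(level='1' wald exact)`. Both parts are needed, because `LEVEL=` alone cannot report a level that is absent from the table.
2. Add a sentence to the prose that the exact interval is reported when an arm is at 0% or 100%.
3. As tidying only, use ACHIEVE in the risk-difference block and label the result as Ziltivekimab minus placebo.

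The cost is a short data step, a few lines of code and one sentence. No data collection, design or testing rule changes.

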3.4.3 Data Plots

Graphical data display for the efficacy parameters will be employed to present observed data and changes from baseline. The Ziltivekimab 15 mg, and Ziltivekimab 30 mg active dose groups as well the placebo group will be superimposed for visual comparison.

A graphical plot for missing data pattern from baseline to end of treatment for the primary efficacy variable (hs-CRP) will also be generated.

3.5 Analysis of Pharmacokinetic and Pharmacokinetic-Pharmacodynamic Modeling

3.5.1 Pharmacokinetic data

A listing of PK blood sample collection times as well as derived sampling time deviations will be provided. A by-patient listing of all serum concentration-time data for each dose group will be presented. Ziltivekimab serum concentrations will be summarized by dose group and nominal time point using appropriate descriptive statistics (eg, n, arithmetic mean, SD, coefficient of variation [CV], minimum, median, maximum, geometric mean, and geometric CV).

For IL-6, results of PK parameters, such as AUC, will be summarized by dose group.

Individual and mean concentration-time profiles will be presented graphically.

3.5.2 Pharmacokinetic-pharmacodynamic modeling

PK-PD model parameters will be derived using plasma IL-6 levels to describe target engagement, with clinically meaningful PD parameters, such as hs-CRP. The specific model parameters to be estimated will be determined based on review of the observed data. The PD parameters to be included in the PD analysis will be determined following review of the study data.

A listing of PD blood sample collection times as well as derived sampling time deviations will be provided. A by-patient listing of all PD results and their corresponding change from Baseline value for each dose group will be presented. The observed and change from Baseline serum results will be summarized using descriptive statistics by dose group.

Graphical presentations, as appropriate for PD variables, may include the following: individual observed and percent change from Baseline serum concentration-time curves for each patient on linear scale and arithmetic mean serum concentration-time curves by dose group on linear scale.

Analysis of pharmacokinetic data and PK-PD modeling will be described in a separate PK-PD analysis plan.

3.6 Safety Assessment

Safety data will be summarized by actual treatment received (and in total for selected analyses) based on the Safety population.

3.6.1 Adverse Events (AEs)

AEs will be captured from the date of informed consent through study completion. All AEs will be coded to system organ class (SOC) and preferred term (PT) using the Medical Dictionary for Regulatory Activities (MedDRA) version 22.0.

A TEAE is defined as an AE that initiated or worsened on or after the date of first dose of study drug up to the end of the Safety Follow-Up Period. For AEs occurring on the first dosing day, if the start time cannot be ascertained, the event will be counted as treatment emergent. These events will be identified in the data by coded terms.

Adverse events of special interest (Section 2.3.4) will be summarized by treatment group and dose.

An overview of AEs will be provided for the following categories including counts and percentages of subjects along with number of events:

- Any TEAEs (overall, by maximum severity, and relationship to study drug)
- Any study drug related TEAEs (overall and by maximum severity)
- Any TEAEs of special interest (overall and by maximum severity)
- Any serious AEs (SAEs) (overall, by maximum severity, and relationship to study drug)
- Any study drug related serious adverse events
- Non-serious adverse events (by maximum severity, and relationship to study drug)
- Any treatment-emergent serious AEs (TESEAEs)
- Any TEAEs leading to study drug interruption
- Any TEAEs leading to study drug discontinuation
- Any AEs leading to death

The number of adverse events and number (percentage) of patients reporting treatment-emergent AEs and SAEs for each preferred term (PT) will be tabulated by System Organ Class (SOC), by SOC and severity, and by SOC and relationship to study drug. If more than one event occurs with the same PT for the same patient, the patient will be counted only once for that PT using the most severe or related occurrence for the summary by severity or relationship to study drug, respectively. The number of events will be presented for overall category of TEAE and for each SOC and PT. The number of events will not be presented for each category of maximum severity and maximum relationship to the study drug.

The number and percentage of patients with TEAEs by occurrence time (0-2, 2-4, 4-6, 6-8, 8-10, 10-12 and >12 weeks) will also be summarized for each preferred term, system organ class, and treatment. The number of patients that completed each time period and the proportion of patients presenting TEAEs in proportion to the number of patients that completed the given time period will also be summarized.

Listings will be presented specifically for SAEs and TEAEs leading to discontinuation of study drug.

3.6.2 Clinical Laboratory Tests

Blood and urine samples for clinical laboratory tests will be collected and processed by a central laboratory.

Values and changes from baseline for lab parameters (excluding efficacy lab parameters) will be presented at each scheduled visit and baseline by laboratory test. The incidence of abnormalities (as defined by normal ranges) prior to the first dose of study drug and after the first dose of study drug will be summarized with counts and percentages of subjects.

All laboratory measurements will be listed.

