APPENDIX B: CLINICAL LABORATORY ANALYTES

Standard Safety Chemistry Panel

Alanine aminotransferase	Albumin
Alkaline phosphatase	Amylase
Aspartate aminotransferase	Bicarbonate (or carbon dioxide)
Blood urea nitrogen	Calcium
Chloride	Creatine kinase
Creatinine	Estimated glomerular filtration rate [1]
Gamma-glutamyl transferase	Glucose
Inorganic phosphorus	Lactate dehydrogenase
Lipase	Potassium
Sodium	Total bilirubin
Total protein	Uric acid
Direct bilirubin	

[1] Estimated glomerular filtration rate will be calculated by CKD-EPI (Chronic Kidney Disease Epidemiology Collaboration) creatinine equation (<https://www.kidney.org/content/ckd-epi-creatinine-equation-2009>).

Hematology

Hematocrit	Hemoglobin
Platelets	Red blood cell count indices [1]
Reticulocyte count	White blood cell count and differential [2]

[1] Red blood cell count indices include mean corpuscular volume and red cell distribution width.

[2] Manual microscopic review is performed only if white blood cell count and/or differential values are out of reference range.

Urinalysis

Albumin	Bilirubin
Blood	Glucose
Ketones	Leukocyte esterase
Microscopy [1]	Nitrite
pH	Protein
Specific gravity	Spot urine protein-creatinine ratio
Urobilinogen	

[1] Microscopy is performed only as needed based on positive dipstick test results.

Endocrinology

β -human chorionic gonadotropin [1]	Follicle-stimulating hormone [2]
[1] Serum pregnancy test will be performed for women of childbearing potential only.	
[2] Postmenopausal women must have had no menstrual bleeding for at least 1 year before initial dosing and either be over the age of 60 years or have an elevated plasma	

follicle-stimulating hormone level (ie, >40 mIU/mL) at Screening.

Lipids and Subfractions

High density lipoprotein-cholesterol
cholesterol Total cholesterol

Low density lipoprotein-
Triglycerides

Infectious Disease Screen

Hepatitis B surface antibody
Hepatitis C antibody

Hepatitis B surface antigen
Human immunodeficiency virus (HIV)-1
and HIV-2

Mycobacterium tuberculosis test

Inflammation and cardiac risk marker

Fibrinogen
NT-pro-BNP

Serum amyloid A,

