2.1.2 Secondary Objectives

The secondary objective is to evaluate the safety of 2 dose levels of Ziltivekimab compared to placebo in patients with NDD-CKD.

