2.2 Study Design

2.2.1 Overview

This is a randomized, double-blind, placebo-controlled study designed to evaluate the efficacy, safety, and PK of Ziltivekimab at 2 dose levels (15 mg or 30 mg) compared to placebo in Japanese patients with Stage 3 to 5 NDD-CKD and evidence of inflammation.

The study will consist of 3 periods: a Screening Period, a Treatment Period, and a Safety Follow-Up Period. The total study duration for each patient will be approximately 6 months.

- Screening Period: up to 2 weeks (Days -14 through -1)
The Screening Period starts on the date of informed consent, and this date will also be the date of the Initial Screening Visit.

- Treatment Period: 12 weeks (Baseline [Day 1] through Week 12)
The Treatment Period starts with the administration of study drug/randomization (Day 1).
- Safety Follow-Up Period: 8 weeks (Weeks 12 through 20)
The Safety Follow-Up Period starts 12 weeks after randomization

Patients will undergo a Screening Period of up to 14 days, during which the inclusion and exclusion criteria will be evaluated. Patients who meet all inclusion criteria and no exclusion criteria will be randomized 1:1:1 to Ziltivekimab 15 mg, Ziltivekimab 30 mg, or placebo (12 patients per group) for a 12-week Treatment Period. Approximately 36 patients will be randomized. Patient randomization will be stratified by CKD stage (3, 4 and 5). There will be approximately 10 sites in Japan.

After the Screening Period, patients will be randomized on Day 1. Randomized patients will receive multiple doses of study drug, and the initial dose of study drug will be administered after all assessments are conducted. Patients will then be followed for efficacy and safety through Week 12 and followed for safety in the Safety Follow-Up Period from Weeks 12 through 20. The primary endpoint evaluation will take place at the End of Treatment (using the average of Week 10 and Week 12 assessments).

Patients will be carefully monitored for 1 to 2 hours at the site post every dosing.

The schedule of procedures can be found in Appendix A of the protocol version 1.3.

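### The eGFR row of the normal-range laboratory table will read about 100% in every arm before and after dosing, and no table counts the patients whose measured eGFR fell

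*SAP*

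**What the plan says.** SAP 3.6.2 plans three outputs for laboratory tests:

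- by-visit values and changes from Baseline, excluding efficacy parameters;
- an abnormality count: "The incidence of abnormalities (as defined by normal ranges) prior to the first dose of study drug" and the same "after the first dose of study drug will be summarized with counts and percentages of subjects";
- a listing of all measurements.

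The section has no shift table, toxicity grade or change-from-Baseline category.

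Protocol 4.1, criterion 2, sets the population: "Stage 3 to 5 NDD-CKD, ie, eGFR >10 and <60 mL/min/1.73 m² using the CKD-EPI" creatinine equation. Protocol Appendix B lists eGFR in the Standard Safety Chemistry Panel, with the footnote "Estimated glomerular filtration rate will be calculated by CKD-EPI". It is not among the efficacy endpoints in SAP 2.3, so the exclusion of efficacy parameters does not remove it.

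The secondary objective (SAP 2.1.2) is to "evaluate the safety of 2 dose levels of Ziltivekimab compared to placebo in patients with NDD-CKD".

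Elsewhere the SAP does count patients by change from Baseline: systolic blood pressure and BMI in 3.6.3, and QTcF in 3.6.4.

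**The concern.** A count of patients outside the normal range is informative only if some patients start inside it. For eGFR the entry criterion rules that out, so the row starts at its ceiling and has nowhere to go if kidney function worsens.

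Safety in non-dialysis CKD is the only secondary objective, and kidney function defines the enrolled population. A fall across a whole arm would show in the planned change summaries. A fall confined to a few patients is harder to see. By-visit minima and quartiles hint at it, but they do not say how many patients fell, or whether the same patients stayed low at the next sample. That is the gap.

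**Working it through.** The plan states no figure for this row, so there is nothing to reproduce. The check is a deduction, followed by two illustrations.

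**1. Deduction**

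- Entry eGFR is above 10 and below 60 for every eligible patient (Protocol 4.1).
- Abnormal means outside the normal range (SAP 3.6.2). The lower limit of normal (LLN) is not in the documents, so I take 60 and 90.
- For any LLN of 60 or more, the screening value is abnormal in every eligible patient: 12/12 per arm. If only the Day 1 value were used, a patient entering just below 60 could read above it, hence about 100%.
- Chemistry is scheduled at Visits 2 to 11, which is 10 post-dose samples. Visits 2, 4 and 6 may become phone visits, leaving 7 (Protocol Appendix A). One abnormal value among these is enough.

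**2. Does the row respond to a true fall?**

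This is an illustrative simulation with 12 patients per arm, entry eGFR uniform from 10 to 60, 8% within-patient variation and 10 post-dose samples. The true fall occurs in one arm only.

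| True fall | Any post-dose value abnormal (LLN 60 or 90) | Last sample abnormal, LLN 60 | Mean change (mL/min/1.73 m²) |
|---|---|---|---|
| 0% | 100% v 100% | 96% v 96% | 0.1 v 0.1 |
| 20% | 100% v 100% | 96% v 100% | 0.1 v -6.9 |
| 30% | 100% v 100% | 96% v 100% | 0.1 v -10.4 |
| 40% | 100% v 100% | 96% v 100% | 0.1 v -13.9 |

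The incidence row does not move, while the planned mean change does. If the normal-baseline numerator of SAP 3.6.3 were borrowed, the row would read 0/12 in every arm, which is equally uninformative.

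**3. A fall in a minority of patients**

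Suppose 2 of 12 patients on active treatment each lose 30% of a baseline of 30, which is 9 units.

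- The arm mean shifts by 2 × 9 / 12 = 1.5 units.
- The standard error of the difference from placebo is SD × √(2/12). For an assumed SD of change of 4, 5 or 6 this is 1.63, 2.04 or 2.45.
- The shift is therefore 0.92, 0.73 or 0.61 standard errors, and the mean-change table would hardly show it.

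**4. Would a threshold count be clean?**

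Use the same SDs and no true change. The chance that one sample shows a fall of 9 or more is Φ(-9/SD), which is 0.0122, 0.0359 or 0.0668. Times 12 patients, that is 0.15, 0.43 or 0.80 false flags per arm at a single visit.

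Over repeated visits I simulated normal error with a shared baseline value (correlation 0.5 between changes). The range in each cell runs from 7 to 10 samples:

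| SD | False flags per 12, any single value | False flags per 12, confirmed at next sample |
|---|---|---|
| 4 | 0.7 to 0.9 | 0.1 |
| 5 | 1.9 to 2.3 | 0.3 to 0.5 |
| 6 | 3.1 to 3.7 | 0.8 to 1.0 |

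These figures depend on the assumed SD and correlation. Confirmation cuts the false flags substantially at every SD shown.

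**5. What the count could show**

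For 2/12 v 0/12, the chance that both events fall in one given arm is C(12,2)/C(24,2) = 66/276 = 0.239. The two-sided Fisher p is 2 × 0.239 = 0.48. The table can only be descriptive.

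**The case against.** The strongest reply is that worsening kidney function is already captured. Protocol 8.6 requires a laboratory abnormality that the investigator judges clinically significantly worse than Baseline, or that leads to a medical intervention, to be reported as an adverse event. Protocol 8.1 treats worsening of a pre-existing condition the same way. SAP 3.6.1 then counts patients by preferred term, severity, relationship and time of onset. SAP 3.1.4 adds median, quartiles, minimum and maximum of change, and every value is listed. Kidney decline is not a named adverse event of special interest, and the trial has 36 patients.

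Most of this stands. A reader might infer that no table counts patients whose kidney function fell. The documents do not support that, because the adverse event tables count those whom an investigator judged to be worse. That judgement has no numeric criterion and is spread over about 10 sites, so only the count by measured value is missing.

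Three other strong readings also fail:

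- **The whole laboratory table is saturated.** Criterion 2 fixes only eGFR. Urea nitrogen, potassium and the other Appendix B analytes are not determined by it.
- **Creatinine is saturated too.** That needs reference limits that the documents do not give, and a value near a limit is not an abnormal one.
- **A threshold table would cleanly show 2/12 v 0/12.** With a single-value rule and the SDs above, noise alone puts an expected 0.7 to 3.7 placebo patients over the line.

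It is also fair to say that the documents do not state whether a calculated value such as eGFR receives a range flag. If it does not, the row is absent and the missing count is the same.

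**Conclusion.** The point holds for one row of one table. Given a laboratory lower limit of 60 or more, the eGFR abnormality rate will be about 100% in all three arms before and after dosing, and so cannot show worsening. With a lower limit below 60 the saturation would be partial.

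This is a gap in descriptive safety reporting. It does not affect the primary analysis or the validity of the other laboratory summaries, and a fall across an arm would still be seen. The impact is low to moderate. It is worth correcting because the measured values are already collected and the SAP already uses change-from-Baseline counts for other safety measures.

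**What to change.** In SAP 3.6.2, add for eGFR a count and percentage of patients by arm with a percent fall from Baseline that is confirmed at the next available sample. The sponsor should fix the cut-offs before unblinding; falls of at least 30% and at least 50% are examples for reporting, not figures from the documents. Set the criterion out in the SAP as the change-from-Baseline criteria in 3.6.3 and 3.6.4 are, but do not carry over their normal-baseline condition on the numerator.

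Three details need stating:

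- the denominator, for example patients with a Baseline and at least two post-dose values;
- what counts as the next sample when a visit was held by phone;
- how a fall first seen at the last sample is shown, since it cannot be confirmed (a separate unconfirmed line would do).

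Do not use a single unconfirmed post-dose value as the main rule. Keep the normal-range table for all other analytes, including creatinine.

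The cost is a few lines of SAP text and one descriptive table. No new sampling is needed, because eGFR is part of the chemistry panel taken at each scheduled site visit.
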